5.4.4.2 Thyroid Function Tests

Thyroid function tests, to be collected every other cycle starting at Cycle 3, should include:

- Thyroid stimulating hormone (TSH)
- Triiodothyronine (T3)
- Free Triiodothyronine (fT3)
- Free thyroxine (FT4)

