5.4 Summary of Statistical Methods

Participants treated at the RP2D in Phase 1b will be included in Stage 1 of the relevant disease-specific cohort for Phase 2. All the data (e.g., safety and efficacy) from these participants will be used in the relevant summary tables and listings for both Phase 1b and Phase 2 (including participants treated at RP2D in Phase 1b).

All relevant participant data will be included in listings. All participants entered into the database will be included in participant data listings. The listings will be generally sorted by first dose level (Phase 1b) or

cohort (Phase 2, including participants treated at RP2D in Phase 1b) and then Participant ID, unless specified otherwise.

All applicable data will be summarized by dose level and overall for Phase 1b, and by cohort and overall for Phase 2 (including participants treated at RP2D in Phase 1b), unless specified otherwise. In addition, data will be summarized by visit and/or time-point when appropriate. Unscheduled or repeat assessments will not be included in summary tables but will be included in listings.

Continuous variables will be summarized using the number of observations (n), mean, standard deviation (SD), median, Q1, Q3, minimum, and maximum along with the total number of patients contributing values.

Descriptive statistics for categorical/qualitative data will include frequency counts and percentages. The total number of participants in the dose level or cohort (N) will be used as the denominator for percent calculations, unless stated otherwise in the table footnote.

Kaplan-Meier model will be used to analyze duration of response, PFS and OS. In all these analyses, in addition to the Kaplan-Meier curve, median, Q1, Q3 and their corresponding CI 95%, number of events and censored cases distribution will be shown.

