5.4.3.4 Clinical Laboratory Evaluation

The following laboratory tests will be performed locally to evaluate the safety profile: serum chemistry (including thyroid tests), hematology (including coagulation), urinalysis, and pregnancy. Except for urinalysis and pregnancy tests which are scheduled at Screening only, the other tests will be performed at Screening, Treatment Phase and End of Treatment (EOT).

For each laboratory parameter, the actual will be summarized and the frequency of participants with clinically significant abnormal laboratory values will be tabulated for baseline and each scheduled post baseline visit, by dose level and overall for Phase 1b and by cohort and overall for Phase 2.

All serum chemistry, hematology and urinalysis data will be listed by participant; the clinically significant abnormal values will be flagged. The pregnancy results will also be listed.

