5.4.6 Missing Data

5.4.6.1 General imputation method

Missing data will not be imputed, and it will be considered as missing values for the analysis.

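### Unless a table footnote overrides SAP 5.4, by-visit percentages of laboratory abnormalities use the full cohort N and shrink as participants leave treatment, fastest in Cohorts 2 and 3.

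*SAP*

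**What the plan says.** SAP 5.4 (Summary of Statistical Methods) states: "Descriptive statistics for categorical/qualitative data will include frequency counts and percentages". It then gives the default denominator: "The total number of participants in the dose level or cohort (N) will be used as the denominator for percent calculations", with the exception "unless stated otherwise in the table footnote". SAP 7 places the table shells, and so presumably their footnotes, in an external document.

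SAP 5.4.3.4 (Clinical Laboratory Evaluation) says that "the frequency of participants with clinically significant abnormal laboratory values will be tabulated for baseline and each scheduled post baseline visit". It gives no denominator of its own.

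Three other provisions bear on this:

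- SAP 5.4.6.1: "Missing data will not be imputed, and it will be considered as missing values for the analysis".
- SAP 5.4, for continuous variables only, promises the usual statistics "along with the total number of patients contributing values". No matching promise is made for categorical counts.
- SAP 5.4: "Unscheduled or repeat assessments will not be included in summary tables but will be included in listings".

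On test timing, Protocol 5.4.4.2 reads: "Thyroid function tests, to be collected every other cycle starting at Cycle 3". Protocol 5.2.3 lists chemistry, hematology and coagulation at the end-of-treatment visit, but not thyroid tests. The schedule in Protocol 5.1 shows thyroid tests at screening and during treatment only.

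**The concern.** Scheduled laboratory tests are done at screening, during treatment and at the end-of-treatment visit. A participant who stops after Cycle 3 cannot contribute a Cycle 9 result, but stays in N. With N as denominator, the Cycle 9 percentage falls with attrition whatever the drugs do.

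Two patterns could then be misread. Within a cohort, a steady abnormality rate among those tested would appear to fade with time. Between cohorts, those that lose participants faster would look cleaner at late visits. Late liver, thyroid and renal abnormalities are of natural interest with this combination, and the by-visit summary is the only laboratory table that SAP 5.4.3.4 describes.

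Thyroid tests have an added scheduling problem. After screening the first test is at Cycle 3, so a participant off treatment before then has no scheduled retest yet remains in the denominator. Unscheduled tests cannot fill the gap, because they are kept out of summary tables.

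**Working it through.** The plan states no figure for this point, so there is nothing to reproduce. The check has two parts.

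**1. Which denominator applies.** SAP 5.4 calls for percentages with categorical counts and makes N the default. SAP 5.4.3.4 names no alternative, and the only stated route to one is a table footnote. On the SAP text alone, N governs the by-visit laboratory table.

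**2. Size of the effect.** By arithmetic:

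printed % = (number abnormal / N) × 100 = (rate among tested) × (tested / N)

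The documents do not give time on treatment. As an assumption, let the share still tested equal exponential PFS at the 6-month rates in SAP 5.1 (null and alternative): 60% and 80% for Cohort 1, 19% and 38% for Cohort 2, 22% and 43% for Cohort 3. With 21-day cycles:

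- t(c) = (c − 1) × 21 / 30.4375 months, giving 1.38, 2.76 and 5.52 months at Day 1 of Cycles 3, 5 and 9
- tested/N = (6-month rate)^(t/6)

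Example, Cohort 2 at 19%, Cycle 9: 0.19^(5.52/6) = 0.217.

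| Cohort (6-month PFS rate) | Cycle 3 | Cycle 5 | Cycle 9 |
|---|---|---|---|
| 1 (60%) | 0.889 | 0.791 | 0.625 |
| 1 (80%) | 0.950 | 0.902 | 0.814 |
| 2 (19%) | 0.683 | 0.466 | 0.217 |
| 2 (38%) | 0.800 | 0.641 | 0.411 |
| 3 (22%) | 0.706 | 0.498 | 0.248 |
| 3 (43%) | 0.824 | 0.678 | 0.460 |

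Now assume that 20% of those tested are abnormal at every visit (an illustration; an assumed 10% halves each printed figure).

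- Cohort 2 at 19%: printed 13.7%, 9.3% and 4.3% at Cycles 3, 5 and 9, with about 25, 17 and 8 of the planned 37 tested.
- Cohort 2 at 38%: 16.0%, 12.8% and 8.2%.
- Cohort 3, 22% to 43%: 14.1–16.5%, 10.0–13.6% and 5.0–9.2%.
- Cohort 1, 60% to 80%: 17.8–19.0%, 15.8–18.0% and 12.5–16.3%.

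So the same 20% at Cycle 9 would print as 12.5% in Cohort 1 and 4.3% in Cohort 2 under the null rates, or 16.3% and 8.2% under the alternatives.

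For thyroid tests, the share off treatment by Cycle 3 Day 1 is 1 − tested/N: 20–32% in Cohort 2 (1 − 0.800 to 1 − 0.683), 18–29% in Cohort 3 (1 − 0.824 to 1 − 0.706) and 5–11% in Cohort 1 (1 − 0.950 to 1 − 0.889). On the protocol schedule these participants would have no post-baseline thyroid result.

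The planned sizes of 45 and 37 count response-evaluable participants; the safety cohorts may be larger. The ratios do not depend on N.

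**The case against.** The strongest reply is that N is only a default. SAP 5.4 allows a footnote to change it, and the footnotes cannot be seen. This stands: whether the final table uses N cannot be settled from the protocol and SAP. It makes the point conditional but does not remove it, because the SAP's own stated rule is unsuitable for this table.

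A reader might go further and infer that the SAP classes untested participants as normal. It does not. SAP 5.4.6.1 keeps missing data missing; the effect arises only through the denominator.

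A reader might also infer that later toxicity as a whole is understated. The documents do not support that. Under Protocol 6.3.6, laboratory abnormalities that are clinically significant, need corrective therapy, or lead to delay, interruption or discontinuation are also recorded as adverse events. SAP 5.4.3.3 summarises those per participant and by maximum grade, where N is suitable, and SAP 5.4.3.4 flags abnormal values in listings. Protocol 6.3.1 prefers a diagnosis to individual signs when events are reported, so the adverse event tables do not fully replace a laboratory table.

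Attrition is also not wholly hidden. Continuous laboratory summaries will show how many contributed, and SAP 5.4.3.1 reports how many participants reached each cycle. A careful reader could rebuild the denominator for numeric parameters, but should not have to.

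The link to the secondary safety endpoint is indirect: that endpoint concerns CTCAE-graded abnormalities, and the by-visit table is not described as graded. No test or decision rule rests on it.

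Finally, the rate among those tested is not the one true rate. It describes participants selected for staying on treatment.

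**Conclusion.** The concern holds in a conditional form. Unless a footnote overrides the default, following the SAP multiplies each by-visit laboratory abnormality percentage by tested/N, which falls with time and falls faster in Cohorts 2 and 3 than in Cohort 1. On the assumed proxy the distortion is large by Cycle 9 in Cohorts 2 and 3, where the printed figure is roughly a fifth to under a half of the rate among those tested. It is more modest in Cohort 1.

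The sizes rest on PFS standing in for time on treatment. Treatment beyond progression (Protocol 4.1.1) would raise retention and stopping for toxicity would lower it. The direction does not depend on the proxy, only on participants leaving over time.

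The effect is confined to by-visit laboratory percentages. Counts, listings and per-participant adverse event summaries are untouched. Confidence is moderate because the footnotes could not be checked.

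**What to change.** First check the laboratory table footnotes in the external tables document. Whatever they say, put the rule in the SAP itself:

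- In SAP 5.4 and 5.4.3.4, state that for tables by visit the denominator is the number of participants with a non-missing result for that parameter at that visit, and print that number beside each percentage. Keep N for participant-level incidence tables.
- Add an any-time post-baseline incidence for each laboratory parameter, among participants with at least one post-baseline value of it. For thyroid tests this shows directly how many were ever retested.

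The cost is a few sentences in the SAP, a column in the by-visit laboratory shells and one further summary. No new data are needed. The drawback is that late-visit percentages will rest on small denominators (about 8 of 37 at Cycle 9 in Cohort 2 under the null proxy) from participants selected for staying on treatment. Printing the number makes that visible.

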5.4.1 Demographics, Other Baseline Characteristics and Medication

5.4.1.1 Demographic Characteristics

Descriptive statistics will be summarized for the demographic characteristics and disease history based on the safety population and efficacy population. Listings will also be presented for the demographic characteristics and disease history, respectively.

The following variables will be described by dose level and overall for Phase 1b and by cohort and overall for Phase 2 (including participants treated at RP2D in Phase 1b) in separate tables: age (years), sex, race, ethnicity, height (cm), weight (kg), and baseline ECOG performance status.

5.4.1.2 Disease History

The following variables for disease history will be summarized by dose level and overall for Phase 1b and by cohort and overall for Phase 2 (including participants treated at RP2D in Phase 1b) in separate tables:

- Primary diagnosis
- Time (months) from the first positive biopsy for this disease to the date of first dose. This will be defined as the number of months between the date of first dose and date of first positive biopsy.
- Histology
- Histological grade
- Metastatic sites at study entry

5.4.1.3 Medical & Smoking History

Medical history will only be listed but not summarized.

The smoking history of each patient will also be described.

5.4.1.4 Prior Systemic Therapy

A listing will be provided for the prior systemic therapy by verbatim term, WhoDrug codification won't be performed.

5.4.1.5 Prior Radiation

A listing will be provided for the prior radiation.

5.4.1.6 Prior Surgery

A listing will be provided for the prior surgery.

5.4.1.7 Subsequent Systemic Therapy

A listing will be provided for the subsequent systemic therapy by verbatim term, WhoDrug codification won't be performed.

5.4.1.8 Subsequent Radiation

A listing will be provided for the subsequent radiation.

5.4.1.9 Subsequent Surgery

A listing will be provided for the subsequent surgery.

5.4.1.10 Prior and Concomitant Medications

All medications, including all prescription, over the counter, herbal supplements and IV medications and fluids, will be recorded on the electronic case report form (eCRF). No coding will be performed for medications.

- Prior medications are defined as medications that started and stopped before the first dose of any investigational product.
- Concomitant medications are defined as medications that continued or started on or after the first dose of any investigational product, up to 30 days after the last dose of investigational product.

Prior and concomitant medications will be listed by verbatim term, WhoDrug codification won't be performed, therefore they will not be summarized; a column will be included in the listing to indicate if the medication is prior or concomitant.

5.4.1.11 Concomitant Procedures

A listing will be provided for the concomitant procedures performed.

5.4.2 Efficacy Analyses

The efficacy analysis is based on tumor assessments, which will be performed with two methods (RECIST 1.1 and iRECIST) at Screening, about every 8 weeks during Treatment Phase and Follow-up. The efficacy analysis will be performed for Efficacy Population.

ORR (and 90% confidence interval by exact distribution), DoR and PFS (Kaplan-Meier estimate) will be estimated for each cohort/group and for each tumor assessment method (by RECIST 1.1 and iRECIST).

The listings by-individual participants will be generated for the detailed tumor assessment, the response assessment by RECIST1.1 and iRECIST, and the derived DoR and PFS.

5.4.3 Safety Analyses

The population used for safety analyses will be the Safety Population. Safety of APX005M in combination with nivolumab will be assessed on the basis of the exposures of investigational products, DLT, AE, laboratory data, vital signs, electrocardiogram (ECG), physical examinations, and Eastern Cooperative Oncology Group (ECOG) performance status.

A TEAE is an AE that occurs after administration of the first dose of the investigational product or a worsening (by CTCAE Grade) of a pre-existent condition, and through 30 days after the last dose of the investigational product, death or initiation of new anticancer therapy, whichever occurs first. SAEs and AEs with potential immunologic etiology will be recorded up to 100 days and pregnancies up to 120 days after the last dose of investigational product, death, or initiation of new anticancer therapy, whichever occurs first.

For AEs, events that occur prior to the first dose of investigational product will be recorded as medical history; events that start after the first dose of investigational product will be recorded on the AE eCRF pages. Thus, all AEs collected from AE eCRF pages are considered as TEAEs.

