6.3 Collection and Reporting

6.3.1 General AE Reporting

All AEs will be collected from the time the subject receives any investigational product through 30 days after receiving the last dose of investigational product, death, or initiation of new anticancer therapy, whichever occurs first. SAEs and AEs with potential immunologic etiology will be recorded up to 100 days and pregnancies up to 120 days after the last dose of investigational product, death, or initiation of new anticancer therapy, whichever occurs first.

Events that occur after the subject signs the informed consent but prior to the first dose of investigational product will be recorded as past medical history; events that start after the first dose of investigational product will be recorded as AEs. In addition, the Investigator should report any AEs that may occur after this time period which are assessed to have a reasonable possibility of being associated with investigational products.

All AEs must be promptly documented on the AE eCRF. The minimum information required for each AE includes event, duration (start and end dates), start time (for events occurring within 48 hours after the start of APX005M infusion) severity, seriousness, causality to investigational product, action taken, and outcome. Whenever possible, reporting specific diagnosis is preferred when reporting AEs in the AE eCRF rather than reporting individual signs and symptoms except for infusion related reactions and cytokine release syndrome.

All AEs that are considered related to investigational products must be followed to resolution, stabilization, until improvement is not expected, 30 days after receiving the last dose of investigational product, death, or initiation of new anticancer therapy, whichever occurs first. SSAR will be followed until resolution, stabilization, or until resolution is not anticipated.

If an office visit is not possible, a follow-up of ongoing AEs should be attempted by telephone and documented in the subject's source file. AEs continuing at 30 days after the last dose of investigational product should have a comment in the source file by the Investigator that the event has stabilized or is not expected to improve.

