5.4.3.3 Adverse Events

All AEs will be collected in the eCRF from the time the participant signs informed consent through 30 days after the last dose of investigational product, death, or initiation of new anticancer therapy, whichever occurs first. AEs will be coded to system organ (SOC) and preferred term (PT) using the MedDRA dictionary v18.0.

The NCI-CTCAE will be used to assess the severity of AEs.

The relationship of each AE to the investigational product will be classified as related or unrelated. If relationship is missing, the event will be listed as missing relationship but summarized as related.

Summaries will focus on the TEAEs. They will be summarized by dose level and overall for Phase 1b and by cohort and overall for Phase 2 (including participants treated at RP2D in Phase 1b). The following summary tables will be provided:

- An overall summary of the frequency of participants reporting all TEAEs, serious TEAEs, TEAEs with CTCAE grade 3 or higher, treatment-related TEAEs (separately for APX005M and nivolumab), and TEAEs leading to treatment discontinuation (separately for APX005M and nivolumab), TEAEs with fatal outcome.
- TEAEs by SOC and PT
- Serious TEAEs by SOC and PT
- TEAEs with CTCAE grade 3 or higher by SOC and PT
- Treatment-related TEAEs by SOC and PT (separately for APX005M and nivolumab)
- TEAEs leading to treatment discontinuation by SOC and PT (separately for APX005M and nivolumab)
- TEAEs with fatal outcome by SOC and PT
- TEAEs by SOC and PT, and by maximum CTCAE grade

All AEs will be listed by dose level (Phase 1b)/cohort (Phase 2, including participants treated at RP2D in Phase 1b), and then study site, participant number, and cycle day. Separate listings will be produced for TEAEs, serious TEAEs, TEAEs leading to APX005M discontinuation, delay, and interruption, and TEAEs with fatal outcome. Separate listings will be generated for immune-mediated events.

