5.4.6.2 Specific imputations

5.4.6.2.1 Partial dates

Only in case of any incomplete dates (missing day) necessary for the analysis, the 15th day of the month and year indicated in each case will be imputed.

Only in case of any incomplete dates (missing day and month) necessary for the analysis, the 15th day of the January year indicated in each case will be imputed.

For instance, Partial AE onset dates will be imputed so that if the partial AE onset date information does not indicate that the AE started prior to treatment or after the TEAE period, the AE will be classified as treatment-emergent.

These data imputations are for categorization purpose only and will not be used in listings.

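### SAP 5.4.3 gives two TEAE rules that conflict for serious and immune-etiology AEs starting 31 to 100 days after last dose, and for later related AEs

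*SAP*

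**What the plan says.** SAP 5.4.3 (Safety Analyses) defines a TEAE as an AE starting after the first dose, or a pre-existing condition that worsens in CTCAE grade, "and through 30 days after the last dose of the investigational product, death or initiation of new anticancer therapy, whichever occurs first". The next sentence sets a longer recording period, 100 days, for serious AEs and AEs of possible immune origin. Protocol 6.3.1 has the same provision: "SAEs and AEs with potential immunologic etiology will be recorded up to 100 days". The following SAP paragraph sends pre-dose events to medical history and post-dose events to the AE eCRF pages, and concludes: "Thus, all AEs collected from AE eCRF pages are considered as TEAEs".

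Three other places in the SAP bear on this:

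- SAP 5.4.3.3 describes AE collection in the eCRF as running from consent "through 30 days after the last dose of investigational product, death, or initiation of new anticancer therapy", with no mention of 100 days.
- SAP 5.4.3.3 also says "Summaries will focus on the TEAEs" and names eight summary tables. It plans a listing of all AEs, and then "Separate listings will be produced for TEAEs, serious TEAEs" and others. For immune events it says "Separate listings will be generated for immune-mediated events", without stating how they are selected.
- SAP 5.4.6.2.1 covers partial onset dates. Where the available part of the date does not show that "the AE started prior to treatment or after the TEAE period, the AE will be classified as treatment-emergent".

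**The concern.** The definition closes the window on time since last dose. The concluding sentence classifies by data source and has no end date. The two agree only if nothing that starts after day 30 reaches the AE pages, and the protocol is written so that some of it does.

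The incidence and severity of AEs is a secondary endpoint (protocol 7.3.2; SAP 2.2.2), and its tables count TEAEs. Protocol 3.7 warns that suspected reactions can appear months after dosing stops, and the 100-day window covers the serious and immune events for which that matters most. The 30-day definition leaves those events out of the tables; the concluding sentence puts them in. Two programmers working correctly from the same SAP could therefore report different serious, Grade 3 or higher, and fatal rates from the same data.

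**Working it through.** There is no planned figure to reproduce. The check is to apply each rule to each onset window.

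**Step 1. Do events after day 30 reach the AE pages?** Yes. Protocol 6.3.1 requires every AE to be documented on the AE eCRF, with seriousness among the required fields. Protocol 5.2.4 has follow-up contacts ask about serious AEs and those of possible immune origin. Protocol 6.3.1 also asks investigators to report AEs arising after the collection period if they may be associated with the products, and gives no end date.

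**Step 2. Apply both rules**, assuming no earlier death or new anticancer therapy:

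| Onset after last dose | Type of AE | On AE pages? | 30-day definition | AE-page sentence |
|---|---|---|---|---|
| Day 0-30 | Any | Yes | TEAE | TEAE |
| Day 31-100 | Serious or immune-etiology | Yes | Not a TEAE | TEAE |
| Day 31-100 | Other, judged possibly related | If reported under protocol 6.3.1 | Not a TEAE | TEAE |
| Day 31-100 | Other, not related | Not normally collected | No conflict | No conflict |
| After day 100 | Judged possibly related | If reported under protocol 6.3.1 | Not a TEAE | TEAE |

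For serious and immune-etiology AEs the rules disagree over 100 - 30 = 70 days. Once new anticancer therapy starts, both recording windows close, and only late related AEs remain in conflict.

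**Step 3. Does another SAP section settle it?** No. The 30-day collection sentence in SAP 5.4.3.3 would make the rules agree, but it contradicts the 100-day recording in SAP 5.4.3 and protocol 6.3.1. It also starts collection at consent, whereas SAP 5.4.3 sends pre-dose events to medical history. The partial-date rule in SAP 5.4.6.2.1 speaks of a TEAE period that an AE can start after. That fits the 30-day definition and not the AE-page sentence, but the section does not state a rule.

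**Step 4. What does one event change?** Take a related fatal pneumonitis starting 45 days after last dose, with no new therapy. Of the eight tables in SAP 5.4.3.3, it belongs in the overall summary, all TEAEs by SOC and PT, serious, Grade 3 or higher, treatment-related, fatal, and maximum grade. The one it does not belong in is discontinuation, because dosing had already ended. So 8 - 1 = 7 tables depend on the rule.

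**Step 5. Size per subject.** If that is the subject's only qualifying event, the rate moves by 1/37 = 2.7 points or 1/45 = 2.2 points. The denominators are the two-stage totals in SAP 5.1, used here as assumptions. They count response-evaluable participants. The safety population is everyone who received both products (SAP 3.2), and participants not evaluable for response are replaced (SAP 2.3.5). In a cohort that completes both stages the safety N may therefore be larger and the shift smaller; a cohort stopped after Stage 1 would have a smaller N.

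**The case against.** The best answer is that there is only one rule. The concluding sentence follows directly from the handling of pre-dose events, so it concerns where the window starts. The only stated end is 30 days, and SAP 5.4.6.2.1 assumes a closed period. On this view the sentence is merely loose, and moving to 100 days is a preference. The account of where the sentence came from is probably right. But the sentence is unqualified, it can be programmed as written, and nothing ranks it below the definition. The choice of 100 days is indeed a recommendation; the need to state one rule is not.

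It is also fair that every AE is listed under either reading, that the safety tables are descriptive, and that ORR and the DLT assessment are untouched. The external TFL document cited in SAP 7 and the eCRF were not seen, and either might specify the rule.

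Two stronger readings are tempting:

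- A reader might infer that SAP 5.4.6.2.1 and the separate listings of all AEs and of TEAEs prove that some AE records must be non-TEAEs. They are consistent with that but do not require it. The partial-date rule is a conditional default that favours inclusion. The two listings could be explained by pre-dose records, since SAP 5.4.3.3 starts collection at consent.
- A reader might infer a large shift in the reported serious-AE rate. That would need a late event rate, the timing of new therapy and the death rate. The documents give none of these, and both death and new therapy shorten the window.

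**Conclusion.** The contradiction is real and lies within SAP 5.4.3. The two statements classify serious and immune-etiology AEs with onset on days 31 to 100, and later related AEs, in opposite ways, and no SAP text says which governs. One such event can change 7 of the 8 named tables, and one subject is worth about 2.7 points at N = 37 or 2.2 at N = 45, with those denominators assumed. The total effect cannot be computed, because the documents give no event counts; it is zero if no such event occurs. It would be wrong to conclude that late events are lost, since they stay in the all-AE listing. What is undetermined is the tabulated rates. This should be corrected before the Phase 2 outputs are final, and it does not affect the primary analysis.

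**What to change.** In SAP 5.4.3, delete "Thus, all AEs collected from AE eCRF pages are considered as TEAEs" and define the TEAE period to match the protocol's recording windows:

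- A TEAE is an AE that starts, or a pre-existing condition that worsens in CTCAE grade, after the first dose and up to 30 days after the last dose.
- For serious AEs and AEs of possible immune origin, the limit is 100 days after the last dose.
- Either window ends earlier at death or at the start of new anticancer therapy.
- Records with later onset are listed and not tabulated, and any related fatal event among them is named in the report text.

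In SAP 5.4.3.3, align the collection sentence: start at first dose, with the same 30- and 100-day limits.

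Select immune-etiology AEs by the rule the sponsor uses for the planned immune-mediated listing, and state that rule in the SAP. Do not add a relatedness requirement, because the 100-day recording rule in protocol 6.3.1 has none. Do not restrict selection to the categories in protocol 3.4.1.2: uveitis is in Table 4 of protocol 3.7 but has no category there. Do not drop infusion reaction/cytokine release syndrome, which that section includes.

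Apply the change to Phase 2 outputs, including participants treated at the RP2D in Phase 1b. Leave the Phase 1b report, made under SAP version 1.0, as it stands.

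The cost is two SAP edits, one derivation in the AE dataset, and writing down a selection rule that the immune-mediated listing needs anyway. No new data, visits or tables are required. The downside is that the window differs by event type, and tabulated rates may look slightly less favourable once late events are counted.
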